5. INVESTIGATIONAL MEDICINAL PRODUCTS

5.1. Enrollment

This is an open-label, single arm study. All eligible subjects will receive open-label E/C/F/TAF. Enrollment and Day 1 Visit cannot occur until subject eligibility has been confirmed.

It is the responsibility of the Investigator to ensure that the subject is eligible for the study prior to enrollment. Once eligibility is confirmed, each subject will be assigned a unique subject number using Interactive Web Response System (IWRS). Once a subject number has been assigned to a subject, it will not be reassigned to any other subject. The subject number assignment may be performed up to 3 days prior to the in-clinic Day 1 Visit, provided that all other screening procedures have been completed and subject eligibility has been confirmed.

Eligibility must be confirmed and all Day 1 tests and procedures must be completed prior to the administration of the first dose of study drug.

IWRS will assign study drug bottle numbers at each study visit. Initiation of study drug must take place on the day of Day 1 Visit.

Post-Week 96

At the End of E/C/F/TAF Visit, the IWRS will assign open-label B/F/TAF FDC.

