3. GENERAL CONSIDERATIONS FOR DATA ANALYSES

The final analysis will include all data collected from the E/C/F/TAF and the B/F/TAF OL extension phases of the study. Separate tables and figures will be created for each phase unless otherwise specified. Data collected from both phases will be included in data listings. Data included in each phase are defined as follows:

E/C/F/TAF Phase Data

- For subjects who are never treated in the B/F/TAF OL extension phase of the study, all available data are considered as the E/C/F/TAF phase data.
- For subjects treated in the B/F/TAF OL extension phase of the study, E/C/F/TAF phase data are defined as data collected **up to** the B/F/TAF OL extension phase first dose date except for data on adverse events (AEs), concomitant medications, pregnancy, and death. For AEs, concomitant medications, pregnancy, and death, only data collected **prior to** the B/F/TAF OL extension phase first dose date are included.

B/F/TAF OL Extension Phase Data

- B/F/TAF OL extension phase data are only available from subjects who enter the B/F/TAF OL extension phase of the study. B/F/TAF OL extension phase data are defined as data collected **after** the B/F/TAF OL extension phase first dose date except for data on AEs, concomitant medications, pregnancy, and death. For AEs, concomitant medications, pregnancy, and death, data collected **on or after** the extension phase first dose date are included.

Analysis results will be presented using descriptive statistics. For categorical variables, the number and percentage of subjects in each category will be presented; for continuous variables, the number of subjects (n), mean, standard deviation (SD) or standard error (SE), median, first quartile (Q1), third quartile (Q3), minimum, and maximum will be presented.

By-subject listings will be presented for all subjects in the All Enrolled Subjects Analysis Set unless otherwise specified, and sorted by subject ID number, visit date, and time (if applicable). Data collected on log forms, such as AEs, will be presented in chronological order within a subject.

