8.3.5. Treatment-Emergent Adverse Events

8.3.5.1. Definition of Treatment-Emergent Adverse Events

E/C/F/TAF phase treatment-emergent AEs are defined as 1 or both of the following:

- Any AEs with an onset date on or after the E/C/F/TAF study drug start date and no later than 30 days after permanent discontinuation of the E/C/F/TAF study drug for subjects who do not participate in the B/F/TAF OL extension phase or the day prior to the date of the first B/F/TAF study drug dose for subjects who participate in the B/F/TAF OL extension phase, or
- Any AEs leading to premature discontinuation of E/C/F/TAF study drug.

B/F/TAF OL extension phase treatment-emergent AEs are defined as 1 or both of the following:

- Any AEs with an onset date on or after the B/F/TAF study drug start date and no later than 30 days after permanent discontinuation of the B/F/TAF study drug, or
- Any AEs leading to premature discontinuation of B/F/TAF study drug.

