8.3.5.2. Incomplete Dates

If the onset date of the AE is incomplete and the AE stop date is not prior to the first dose date of E/C/F/TAF study drug, then the month and year (or year alone if month is not recorded) of onset determine whether an AE is treatment emergent.

The event is considered treatment emergent for the E/C/F/TAF phase if both of the following 2 criteria are met:

- The month and year (or year) of the AE onset is **the same as or after** the month and year (or year) of the first dose date of E/C/F/TAF study drug, and
- The month and year (or year) of the AE onset is **the same as or before** the month and year (or year) of the date corresponding to the minimum of (1) the last dose of E/C/F/TAF study drug plus 30 days AND (2) the first dose of B/F/TAF study drug minus 1 day

The event is considered treatment emergent for the B/F/TAF OL extension phase if both of the following 2 criteria are met:

- The month and year (or year) of the AE onset is **after** the month and year (or year) of the first dose date of B/F/TAF study drug, and
- The month and year (or year) of the AE onset is **the same as or before** the month and year (or year) of the date corresponding to 30 days after the date of last dose of B/F/TAF study drug

An AE with completely missing onset and stop dates, or with the onset date missing and a stop date on or after the first dose date of E/C/F/TAF study drug, will be considered to be treatment emergent for the E/C/F/TAF phase. In addition, an AE with the onset date missing and incomplete stop date with the same or later month and year (or year alone if month is not recorded) as the first dose date of E/C/F/TAF study drug will be considered treatment emergent.

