- b) Last Study Date is the maximum of nonmissing study drug start dates and end dates, clinic visit and laboratory visit dates, including the 30-day follow-up visit date for subjects who prematurely discontinued study or who completed study according to study completion eCRF. Please note: if study drug start date or end date is partially missing, the imputed date (day imputed as 15) will be used. If subject died and the death date is complete (ie, not partial date) and before the imputed last study date, the complete death date should be used as the imputed last study date. Note that last visit date and last lab date include the 30-day follow-up visit.

14) Toxicity Grades:

- a) With regards to Triglycerides and Hypercholesterolemia, if the fasting status is not 'Y', in other words it is blank or 'N', then the lab result value would not be graded as non-fasting values are not interpretable.
- b) For toxicity grade summary, we will include all postbaseline graded results up to 30 days after the last dose of study drug, not just those at summarized visits.

15) Clarification of the following LOCF algorithms:

- Baseline values will not be carried forward.
- For CD4: If a value is missing in an analysis visit window, replace the missing value with the last on-treatment value observed before the analysis visit window that has the missing value.

16) For safety ECGs at postbaseline visits, the most conservative (worst) value within the window will be selected, eg, abnormal will be selected over normal for safety ECG or clinically significant abnormal will be selected over not clinically significant normal if there are multiple abnormal findings.

17) Treatment-Emergent Adverse Events

Events with Missing Onset Day and/or Month

The event is treatment emergent for the E/C/F/TAF phase if the following 3 criteria are met:

- The month and year (or year) of onset date is the same as or after the month and year (or year) of the first dose of E/C/F/TAF study drug, and
- The month and year (or year) of the onset date is the same as or before the month and year (or year) of the date corresponding to the minimum of (1) the last dose of E/C/F/TAF study drug plus 30 days AND (2) the first dose of B/F/TAF study drug minus 1 day, and
- End date is as follows:

The (complete) end date is on or after the first E/C/F/TAF dose date, or

The month and year (or year) of end date is the same or after the month and year (or year) of the first dose of E/C/F/TAF study drug, or

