End date is completely missing

The event is treatment emergent for the B/F/TAF OL extension phase if the following 3 criteria are met:

- The month and year (or year) of onset date is after the month and year (or year) of the first dose of B/F/TAF study drug, and
- The month and year (or year) of the onset date is the same as or before the month and year (or year) of the date corresponding to the last dose of B/F/TAF study drug plus 30 days, and
- End date is as follows:

The (complete) end date is on or after the first B/F/TAF dose date, or

The month and year (or year) of end date is the same or after the month and year (or year) of the first dose of B/F/TAF study drug, or

End date is completely missing

Events with Completely Missing Onset Date

An AE with a completely missing onset date is defined as TEAE for the E/C/F/TAF phase if end date is as follows:

- The (complete) end date is on or after the first E/C/F/TAF dose date, or
- The month and year (or year) of end date is the same or after the month and year (or year) of the first dose of E/C/F/TAF study drug, or
- End date is completely missing

18) Calculation of ratios

To calculate laboratory ratios (eg, fasting total cholesterol to HDL ratio), lab value of each test in the ratio needs to be from the same accession number; if any test value used for the ratio calculation from the same accession number is missing, the ratio is not calculable (ie, missing).

19) Graded Laboratory Abnormalities Summary

The following labels will be used for treatment-emergent laboratory abnormalities and treatment-emergent Grade 3 or 4 laboratory abnormalities summary tables and listings:

Battery	Lab Test Label Used in l-labtox Listing	Toxicity Direction	Lab Test Label Used in t-labtox Table
Hematology	Hemoglobin	Decrease	Hemoglobin (Decreased)
	Neutrophils	Decrease	Neutrophils (Decreased)
	Platelets	Decrease	Platelets (Decreased)
	WBC	Decrease	WBC (Decreased)
Chemistry	Albumin	Decrease	Albumin (Decreased)
	Alkaline Phosphatase	Increase	Alkaline Phosphatase (Increased)
	ALT	Increase	ALT (Increased)
	Amylase	Increase	Amylase (Increased)
	AST	Increase	AST (Increased)
	Bicarbonate	Decrease	Bicarbonate (Decreased)
	Corrected Calcium	Increase	Corrected Calcium (Hypercalcemia)
	Corrected Calcium	Decrease	Corrected Calcium (Hypocalcemia)
	Creatine Kinase (CK)	Increase	Creatine Kinase (Increased)
	Creatinine	Increase	Creatinine (Increased)
	GGT	Increase	GGT (Increased)
	Lipase	Increase	Lipase (Increased)

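### If B/F/TAF starts on the 1st of a month, an adverse event with a partial onset date in that month is treatment-emergent for neither phase

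*SAP*

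**What the plan says.** With complete dates the rule is simple. SAP 8.3.5.1 makes treatment-emergent for the extension "Any AEs with an onset date on or after the B/F/TAF study drug start date", up to 30 days after permanent discontinuation. A second route, whatever the onset date, is "Any AEs leading to premature discontinuation of B/F/TAF study drug". SAP Section 3 agrees: AE data collected on or after "the extension phase first dose date are included" in the B/F/TAF phase.

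With partial onset dates, SAP 8.3.5.2 and Appendix 7 item 17 compare months (or years) instead of days:

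- **E/C/F/TAF phase:** the onset month (year) may be no later than that of the earlier of two dates: "1) the last dose of E/C/F/TAF study drug plus 30 days AND (2) the first dose of B/F/TAF study drug minus 1 day".
- **B/F/TAF phase:** the requirement is that the "onset date is after the month and year (or year) of the first dose of B/F/TAF study drug". The same month (year) does not qualify.

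The fallback for missing onset covers only completely missing dates and assigns those to E/C/F/TAF.

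**The concern.** The two partial-date rules are meant to meet, with start-month events going to E/C/F/TAF. They meet only if the day before the first B/F/TAF dose lies in the same month (year) as the dose itself. When it does not, an event recorded only by that month (year) has no phase.

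Uncertainty about the day cannot justify this. With a start on the 1st, every day of the month is on or after the first-dose date. It is also within 30 days of it (1 + 30 = 31), so under 8.3.5.1 any complete date in that month would be a B/F/TAF treatment-emergent event.

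B/F/TAF safety on hemodialysis is a secondary objective, reported through the tables of SAP 8.3.6. An event lost this way is missing from all of them unless it led to B/F/TAF discontinuation. The error runs one way only: it removes events that belong to the B/F/TAF phase.

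**Working it through.** The plan gives no figure on this point, so the check applies the rules as written.

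**Where the hole is.** Let F be the first B/F/TAF dose date and P(d) the month-and-year (or year) of a date d. Assume the last E/C/F/TAF dose falls on the day before F or on F. The minimum in the E/C/F/TAF rule is then F − 1, and:

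- E/C/F/TAF requires P(onset) ≤ P(F − 1).
- B/F/TAF requires P(onset) > P(F).
- Neither phase applies if P(F − 1) < P(onset) ≤ P(F).

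The last line can be met only if F − 1 and F lie in different months (years). That means a start on the 1st of a month, or on 1 January for year-only dates.

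| First B/F/TAF dose | Recorded onset | E/C/F/TAF bound | E/C/F/TAF | B/F/TAF |
|---|---|---|---|---|
| 1 Sep 2018 | Sep 2018 | Aug 2018 | no | no |
| 2, 15 or 30 Sep 2018 | Sep 2018 | Sep 2018 | yes | no |
| 1 Jan 2019 | 2019 | 2018 | no | no |
| 2 Jan 2019 | 2019 | 2019 | yes | no |

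Running both rules over every start date in 2018 and 2019 gives the same answer. All 24 first-of-month starts leave a hole for month-only dates and no other start does. For year-only dates, only the two 1 January starts do.

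**Size.** Assumptions: no dosing gap, start dates equally likely over 365 days, and onsets uniform over B/F/TAF treatment plus 30 days (336 + 30 = 366 days, or 420 + 30 = 450 days). Shares are of onsets recorded month-only or year-only, not of all onsets.

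- Month-only, start dates affected: 12/365 = 3.3%.
- Month-only, share lost for those subjects: 28/366 = 7.7% to 31/366 = 8.5% (450 days: 28/450 = 6.2% to 31/450 = 6.9%).
- Month-only, average over all starts: the 12 months hold 365 days, so 365/(365 × 366) = 0.27% (450 days: 1/450 = 0.22%).
- Year-only: 1/365 start dates, losing 365/366 = 99.7% of that subject's year-only onsets (450 days: 365/450 = 81.1%). The averages are again 0.27% and 0.22%.

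**Chance that anyone starts on a 1st.** This is 1 − (353/365)^n for n entrants: 28% for n = 10, 63% for n = 30, 80% for n = 48. The number entering is not given. The ceiling of 48 is 55 treated minus at least 7 who had stopped study drug by the Week 48 window (Protocol 1.2.5); early stoppers are not eligible (Protocol 6.4.2).

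**Check of the fix.** With the added condition, all 2018 start dates, both durations and both kinds of partial date give 0 of 365 starts with a hole, 0 onset days flagged for both phases and 0 earlier onset days moved into B/F/TAF. For leap year 2020, 12/366 (month-only) and 1/366 (year-only) starts have a hole before the change and none after.

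**The case against.** The strongest reply is that this hardly ever matters. It needs a first-of-month start and an unresolved partial onset in that month, and nothing in the documents shows that a partial AE date will remain. Source records must hold AE start dates and discrepancies are queried (Protocol 9.1.5 and 9.1.6). As an illustration with assumed inputs, 30 subjects with 6 AEs each and 5% month-only onsets give 30 × 6 × 0.05 × 0.00273 = 0.025 expected lost events. With 48 subjects, 10 AEs each and 10%, it is 0.13. The 28% to 80% figures are the chance of a first-of-month start, not of a lost event. The ceiling of 48 is also loose, because the bridge after Week 96 is described for US subjects only. All of this stands.

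Serious, severe and related events also stay visible, since SAP 8.3.6 lists them separately without restriction to treatment-emergent events. That stands too, but the tables would still be wrong.

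A further point is that the fix recovers little. On the same assumptions, month-only onsets in the start month on or after the first dose average 5738/365 = 15.7 days of 366 (4.3%). The fix returns 1.0 of these to the B/F/TAF phase; the rest are counted under E/C/F/TAF. That is so, but those events are counted somewhere. Assigning them to E/C/F/TAF is an allocation choice that is not criticised here.

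Finally, an event on the first-dose date might precede the dose itself. SAP 8.3.5.1 works by date, however, and counts that day as B/F/TAF.

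**Conclusion.** The concern holds. As written, the partial-date rules drop an event from both phases when B/F/TAF starts on the 1st of a month (1 January for year-only dates), against the SAP's own complete-date rule and its phase definition. That result rests on the text alone.

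The size rests on the uniform-start and uniform-onset assumptions above and is small. The number of records affected is unknown and may be zero. The primary endpoint and efficacy are untouched. The year-only case adds little in practice.

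The same hole opens for other start days if the last E/C/F/TAF dose plus 30 days ends in an earlier month or year than the B/F/TAF start. That is not the planned switch, since Protocol 5.1 says "At the End of E/C/F/TAF Visit, the IWRS will assign open-label B/F/TAF FDC".

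**What to change.** In SAP 8.3.5.2 and Appendix 7 item 17, add that an AE is also treatment-emergent for the B/F/TAF phase if all three hold:

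- its partial onset is in the same month and year (or the same year, if only the year is known) as the first B/F/TAF dose;
- it meets the B/F/TAF upper bound and end-date criteria of Appendix 7 (for a full stop date, "The (complete) end date is on or after the first B/F/TAF dose date");
- it does not meet the E/C/F/TAF partial-date rule.

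Leave the rest unchanged. A supplementary B/F/TAF count that also takes in other switch-month or missing-onset events is optional.

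The cost is one condition in two places and one programming line. The third condition prevents double counting. Only in an unplanned gap of more than 30 days between regimens could an off-drug onset in the start month be counted under B/F/TAF. If the SAP is already final, its Section 1 provides for documenting the change in the final clinical study report.

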8. SAFETY ANALYSES

Safety data will be summarized for the subjects in the E/C/F/TAF Safety Analysis Set and the B/F/TAF Safety Analysis Set. All safety data will be included in data listings.

The primary endpoint of the incidence of treatment-emergent Grade 3 or higher AEs up to Week 48 was conducted for the Week 48 clinical study report and will not be repeated for this final analysis.

The secondary endpoint of the incidence of treatment-emergent Grade 3 or higher AEs up to Week 96 is defined in a similar manner to the primary endpoint included in the Week 48 clinical study report (See Section 8.1).

E/C/F/TAF Phase

For subjects who do not participate in the B/F/TAF OL extension phase, all safety data collected from the first dose of E/C/F/TAF up to 30 days after permanent discontinuation of E/C/F/TAF study drug will be summarized, unless specified otherwise. For subjects who participate in the B/F/TAF OL extension phase, all safety data collected up to the date of the first B/F/TAF study drug dose will be summarized, unless specified otherwise.

B/F/TAF OL Extension Phase

All safety data collected from the first dose of B/F/TAF up to 30 days after permanent discontinuation of B/F/TAF study drug will be summarized, unless specified otherwise.

8.1. Adverse Events Up to Week 96

Adverse events up to Week 96, or adverse events on or prior to Week 96, refers to those adverse events with onset date (if applicable) on or prior to the date of the Week 96 visit, as recorded on the Visit Date CRF, for subjects who had the Week 96 visit performed according to the Visit Date CRF.

If the onset date of an AE is partially missing (with only year and month or year alone), the event is considered on or prior to Week 96 if the month and year (or year alone) of the AE onset date is the same as or before the month and year (or year) of the Week 96 visit date recorded on the Visit Date CRF.

If the onset date of an AE is completely missing, the event is considered on or prior to the Week 96 if any of the following three criteria are met:

- The AE stop date is on or prior to the Week 96 visit date; or
- The AE stop date is partially missing, with the month and year (or year alone) on or prior to the Week 96 visit date; or
- The AE stop date is completely missing, including the case when AE is still ongoing.

For subjects who prematurely discontinued the study prior to the Week 96 visit, all adverse events will be considered AEs on or prior to Week 96.

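### Unless it led to stopping B/F/TAF, an adverse event with no onset date is never counted as B/F/TAF treatment-emergent, even if first collected, ended or ongoing on that drug.

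*SAP*

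**What the plan says.** Two places in the SAP handle an adverse event whose onset date is completely missing.

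- **SAP 8.3.5.2.** If the stop date is also missing, or falls on or after the first E/C/F/TAF dose, the event "will be considered to be treatment emergent for the E/C/F/TAF phase". If the stop date is incomplete, an event whose stop month or year is the same or later "as the first dose date of E/C/F/TAF study drug will be considered treatment emergent"; no phase is named there.
- **SAP Appendix 7, item 17.** "An AE with a completely missing onset date is defined as TEAE for the E/C/F/TAF phase if end date is as follows". The first of three alternatives is "The (complete) end date is on or after the first E/C/F/TAF dose date, or"; the others are a partial end date in the same or a later month or year, and a completely missing end date.

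Neither place gives a B/F/TAF rule for this case. Three other provisions bear on it.

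- **SAP 8.3.5.1.** "B/F/TAF OL extension phase treatment-emergent AEs are defined as 1 or both of the following": an onset-date window, or "Any AEs leading to premature discontinuation of B/F/TAF study drug". The second criterion needs no onset date.
- **SAP 3.** For adverse events, E/C/F/TAF data are those collected before the first B/F/TAF dose. For the extension, data collected on or after "the extension phase first dose date are included".
- **SAP 8.1.** An event with no onset date counts as on or before Week 96 if its stop date is on or before that visit, fully or by month and year, or if "The AE stop date is completely missing, including the case when AE is still ongoing".

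**The concern.** Safety and tolerability of B/F/TAF on hemodialysis is a stated secondary objective (Protocol 2, SAP 1.1). No formal testing is planned (SAP 3.5), so the event counts are the evidence. A rule that sends every undated event to the earlier drug, including one nobody recorded until the subject was on the later drug, takes events away from the drug the extension was added to study.

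The SAP does not treat the two phases this way elsewhere. For lipid-modifying drugs with an unknown start date, Appendix 7 item 21 writes one rule per phase. A graded laboratory abnormality with a missing baseline is treatment-emergent in whichever phase it falls (SAP 8.4.2.1), and a missing causality assessment is summarized as related (SAP 8.3.3). For a partial onset date, the E/C/F/TAF assignment is capped at the day before the first B/F/TAF dose, at month or year level. Only the completely missing onset has neither a cap nor a B/F/TAF counterpart.

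**Working it through.** The plan gives no figure on this point, so the check is to apply the rules case by case and then bound the step size.

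**1. Rollover subject, onset completely missing.** Flags under SAP 8.3.5.1, 8.3.5.2 and item 17. Ongoing is treated as a missing stop date, as SAP 8.1 does.

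| End date | Led to B/F/TAF discontinuation? | E/C/F/TAF flag | B/F/TAF flag |
|---|---|---|---|
| Before first E/C/F/TAF dose | No | No | No |
| During E/C/F/TAF | No | Yes | No |
| During B/F/TAF | No | Yes | **No** |
| Ongoing or missing | No | Yes | **No** |
| During B/F/TAF | Yes | Yes | Yes |
| Ongoing or missing | Yes | Yes | Yes |

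The two bold cells are the problem when the event was first collected on B/F/TAF.

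**2. Set against SAP 3.** Such an event is extension-phase data carrying only an E/C/F/TAF flag. If the flag governs, it is tabulated under E/C/F/TAF. If the phase split governs, it is outside the E/C/F/TAF data and unflagged for B/F/TAF, so it is in neither phase's treatment-emergent tables. The SAP does not say which governs. Under either reading it is absent from the B/F/TAF tables.

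**3. Week 96 endpoint.** An undated Grade 3 or 4 event reaches it only if two conditions hold: its stop date is missing, ongoing, or at or before Week 96 (SAP 8.1), and SAP 3 does not exclude it. A known stop date after the Week 96 visit keeps it out.

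**4. Step size.**
- Treated with E/C/F/TAF: 55 (SAP Appendix Table 1).
- Discontinued study drug by the Week 48 window: at least 7 (Protocol 1.2.5, interim results).
- Early discontinuers cannot roll over (Protocol 6.4.2 and 6.5.2).
- Largest possible B/F/TAF set: 55 − 7 = 48.
- Smallest step for one subject in a B/F/TAF row: 1/48 = 2.1 points.
- Step for one subject in an E/C/F/TAF row: 1/55 = 1.8 points.

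The actual extension size is not given. Under assumed sizes, the step is:

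| Assumed B/F/TAF subjects | Points per subject (100/n) |
|---|---|
| 5 | 20.0 |
| 10 | 10.0 |
| 20 | 5.0 |
| 30 | 3.3 |
| 40 | 2.5 |

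The step occurs only if the undated event is the subject's sole event in that row, because SAP 8.3.6 counts each subject once per summary.

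**The case against.** The case against has several parts.

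- **Rarity.** Source records must hold event start and end dates (Protocol 9.1.5), entries are source-verified and queried (Protocol 9.1.6), and adverse events are reviewed at every extension visit (Protocol 6.4.3). An onset without even a year should be uncommon. This stands, and it limits the likely effect.
- **Visibility.** All events from both phases are listed with a treatment-emergent indicator (SAP 3, 8.3.6). This also stands, but a listing does not correct a table.
- **Consistency.** For partial dates, an onset in the month of the first B/F/TAF dose also goes to E/C/F/TAF, so the plan could be said to allocate each event to one phase and resolve ties to the earlier drug. That explains a tie. It does not explain assigning to E/C/F/TAF an event first collected well into the extension, which SAP 3 places in the extension.
- **Dilution.** In the interim E/C/F/TAF data, 92.7% of subjects (51 of 55) had at least one event. If B/F/TAF is similar, the any-event row will rarely move. This stands for that row; rows by preferred term or for Grade 3 or 4 events are more exposed.

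A reader might also infer more than the documents support. It is not true that an undated event can never count for B/F/TAF, because the discontinuation criterion catches some. Nor can B/F/TAF rates overall err only downward: the month-level upper bound for partial onset dates can admit an onset later than 30 days after the last dose.

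**Conclusion.** The point holds as a defect in a stated rule and a conflict with SAP 3. Apart from events leading to premature B/F/TAF discontinuation, an event with no onset date cannot enter the B/F/TAF treatment-emergent tables, whatever its end date and whenever it was first collected. The effect of this one rule on B/F/TAF incidence is downward or nil.

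The total size cannot be determined from the documents. The figure of 2.1 points is a floor on the step for a subject whose row status changes. It is not a loss that every affected subject causes; for a subject with another qualifying event in the row the change is zero. A reader might also infer that these events automatically inflate the Week 96 E/C/F/TAF endpoint. They do so only under the two conditions in step 3 of the working.

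The conclusion assumes that ongoing is handled as a missing stop date outside SAP 8.1 as well, and that collection in SAP 3 refers to when the event was recorded, which the SAP does not spell out.

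**What to change.** In SAP 8.3.5.2 and Appendix 7 item 17:

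1. Add that, for rollover subjects, an event with a completely missing onset date is B/F/TAF treatment-emergent if it was first collected on or after the first B/F/TAF dose **and** its end date (or known month and year) is on or after that dose, ongoing or missing.
2. State that an event already recorded before the first B/F/TAF dose, or ended before it, belongs to E/C/F/TAF only. Without the collection-date condition, an undated event known to pre-date B/F/TAF and still ongoing would be counted against it.
3. State whether an undated event first collected in the extension also keeps its E/C/F/TAF and Week 96 flags, consistent with SAP 3.
4. Restate the discontinuation criterion in item 17, and flag these events in the listing.

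The cost is a few sentences and a programming condition. It needs a date of first recording for each event; the documents do not say which field holds it. The downside is that a rare undated event that began on E/C/F/TAF but was first reported in the extension may be counted for B/F/TAF.
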